**NCT #: NCT04870710**

**January 2nd, 2022**

Protocol Number:	2019P001016
Title:	Feasibility Electrical Stimulation Study for Visual Hallucinations
Design:	Open Label, Non-randomized, Crossover Design with Baseline, Day 5 and 1 Month follow up visits during which tES (Cathodal tDCS & 2hz tACS) were delivered to the visual cortex from Baseline to Day 5 each day (5 days) twice a day for 20mins. Participants first entered the cathodal tDCS condition first and then after a washout period (~2 weeks) entered the 2hz tACS condition to test the effectiveness and feasibility of stimulating the visual cortex using a novel targeting methodology consisting of a lesion network guided brain target near V5/MT.
Objectives:	
Enrollment:	10 Individuals
Clinical Sites:	Beth Israel Deaconess Medical Center, Boston, MA
Patient Population:	Male or female outpatients 18-50 years of age patient's diagnosis with either schizophrenia, schizoaffective disorder, or psychotic bipolar as defined by DSM-5 or DSM-IV-TR criteria
Primary and Secondary Outcomes:	Primary Outcomes: Steady-State Visual Evoked Potentials (SSVEP); Positive and Negative Syndrome Scale (PANSS); Biological Motion Secondary Outcomes: Global Assessment of Functioning (GAF); Velocity Discrimination; International Affective Picture System (IAPS) Task; Montgomery-Asberg Depression Rating Scale (MADRS)
Inclusion Criteria:	
 
1. Meet diagnostic criteria for schizophrenia, schizoaffective disorder, or psychotic bipolar disorder as verified by the Structured Clinical Interview for Diagnostic and Statistical Manual of Mental Disorders, 4th Edition, Text Revision (DSM-IV TR) and consensus clinical diagnosis;
 
2. had no changes to relevant anti-psychotic medications for a period of 1 month prior to participation;
 
3. had a sufficient level of English to allow participation.
 
4. 18-50 years of age
 
 
In addition to the criteria above, participants for this stimulation procedure will be included if they have a history of VH or experiencing moderate symptoms of VH; had no changes to relevant anti-psychotic medications for a period of 1 month prior to participation; and do not have a history of moderate-to-severe visual impairment secondary to glaucoma, cataract or macular degeneration. Additionally, individuals will need to score above 20 on the Mini Mental Status Examine to be included in the study.

Exclusion Criteria:	
 
1. metal implants in head.
 
2. implanted electronic devices.
 
3. history of neurological problems, seizure or head injury.
 

	
4. skin sensitivity.
 
5. claustrophobia.
 
6. organic brain syndrome
 
7. intellectual disability or other cognitive dysfunction that could interfere with capacity to engage in study as determine by the PI
 
8. a history of substance or alcohol abuse or dependence (other than nicotine) in the last 6 months or otherwise unable to commit to refraining from alcohol use during the acute period of study participation. The acute period of study participation is defined as during their visit and 24 hours before and after their visit.
 
9. Significant suicidal ideation or those who have enacted suicidal behaviors within 6 months prior to intake will be excluded from study participation and referred for appropriate clinical intervention.
 
10. Serious medical illness or instability requiring hospitalization within the next year.
 
11. Experience with any cardiac event.
 
12. Pregnant women, lactating women, women who are breastfeeding and women of childbearing potential who are not using medically accepted forms of contraception (e.g., IUD, oral contraceptives, barrier devices, condoms and foam, or implanted progesterone rods stabilized for at least 3 months).

Statistical Methodology:	
Within and Between comparisons to statistical detect differences in symptoms, visual tasks and electrophysiology measures before and after treatment conditions (cathodal tDCS and 2hz tACS). To determine the effectiveness and feasibility of targeting the visual cortex with a novel targeting methodology to engage target outcomes

**Statement:** The design, conduct and reporting of this trial shall be conducted in accordance with the protocol, the United States 45 Code of Federal Regulations (CFR) part 46 known as “The Common Rule”, 45 CFR 164.502(d), and 164.514(a)-(c) known as “The Privacy Rule” of the Health Insurance Portability and Accountability Act (HIPAA), and the International Conference on Harmonization (ICH)/Good Clinical Practice (GCP). All Investigators will have documented training in The Collaborative Institutional Training Initiative (CITI Program) in Biomedical Research and GCP.

[figure not shown]
**Background:** Functional neuroimaging studies have identified neural correlates of VH across multiple brain regions and support hypotheses that increased visual cortex activity and sensory cortex over-stimulation generate VH (Zmigrod et al., 2016, Manford et al., 1998, Allen et al., 2008, Ffytche et al 2008). Using lesion network mapping, researchers found that the extrastriate visual cortex was causal linked to the development of (Kim et al., 2019). The association between extrastriate visual cortex activation and VH would suggest this region may be optimal for modulation via brain stimulation. While tDCS is a promising adjunctive treatment of auditory hallucinations and negative symptoms in schizophrenia, less is known about its role in treating VH. To date, two cases have been described where cathodal tDCS over the occipital area was applied to patients experiencing treatment refractory VH, and this resulted in symptomatic improvement (Shiozawa et al., 2013, Koops et al., 2017).

**Transcranial Electrical Stimulation (tES):** tES is a non-invasive brain stimulation technique which modulates cortical excitability by a weak electrical current [< 4 milliamps (mA)] between two electrodes via direct current (DC), alternating current (AC), random noise (RN) or oscillatory current (OC). This study will utilize cathodal tDCS and 2hz tACS. Five days twice a day tES will be

**Electroencephalography (tES):** EEG is a routine, non-invasive procedure to record brain activity. EEG electrodes will be attached to the skin, indirectly. Most of the electrodes are mounted in an elastic cap, which is fitted over the head and held in place with elastic straps. Some additional electrodes are placed next to the eyes, on the forehead, or behind the ears, and are held in place with adhesive collars. Electrical contact between the skin and the electrodes is achieved via a water-soluble electrode gel.

**Study Rationale:** The visual system is an important site of pathology in patients with schizophrenia, schizoaffective disorder, bipolar disorder, Parkinson’s disease, Lewy body dementia, Charles Bonnet syndrome, and brain lesions experiencing visual hallucinations. Visual symptoms are associated with worse poorer outcome and treatment refractoriness. A recent study identified a causal location in the extrastriate visual cortex with visual hallucinations (VH). Two case studies have found that transcranial electrical stimulation of the occipital cortex improved VH in treatment refractory patients with visual hallucinations. While promising it is unclear whether the symptom reductions resulted from activity changes in the visual cortex or not. Here we aim to answer the question whether high definition transcranial direct current stimulation when optimally targeted to a specific brain region (extrastriate visual cortex) can engage the target and improve behavioral symptoms.

## Study Protocol:

## Study Timeline

	Baseline	Day 2	Day 3	Day 4	Day 5	1-Month
EEG (IAPS, SSVEP)	X				X	X
Clinical Assessments	X				X	X
Questionnaires	X				X	X
Visual Tasks	X				X	X
Cognition	X				X	X
tES Treatment	X	X	X	X	X	
Sensation Questionnaire	X	X	X	X	X	

### **Study Visits and Details:**

Participants will complete baseline clinical, neuropsychological, visuoperceptual and neurophysiological assessments (day 0), short-term follow-up (day 5) and long-term follow-up (month 1).

#### **Pre-Screening**

Subjects will be prescreened. If the subject appears to qualify for the study, they will be invited in for a screening and baseline visit.

#### **Screening and Baseline Procedures (approximately 3-4 hours)**

Screening and baseline procedures will be conducted in the Massachusetts Mental Health Center (MMHC)/ Beth Israel Deaconess Boston. The urine toxicology screen and pregnancy test will be completed at MMHC or within Beth Israel Deaconess Boston.

- Eligibility pre-screen will include a telephone pre-screening questionnaire that will assess basic inclusion and exclusion criteria.

- Eligibility screen will include a screening questionnaire that will assess more details related to inclusion and exclusion criteria and will be conducted in-person during the clinical diagnostic session (i.e., the first visit to the laboratory).

- Informed consent will be obtained

- Urine toxicology screen

- Urine pregnancy testing for females of childbearing age

**Subjects will be informed that if they do not pass the urine toxicology screen (other than prescribed medication), they will be withdrawn from the study and will not receive compensation for the initial visit. This will be made clear in the pre-screening questionnaire.**

- tES screening questions for tES participation

- Demographics: Subjects will be asked to provide standard demographic information (age, sex, race/ethnicity, level of education, cohabitation status) using forms employed in previous studies.

- Psychiatric, medical, substance use history and medication review

- Signing a release to allow for access to recent psychiatric records, if confirmation of medications or psychiatric history is necessary

- If subjects have previously had a structural MRI performed through BSNIP2, they will be asked for permission to review these scans for use in neuronavigation.

## **OBJECTIVES**

### **Primary Objective**

The primary objective of this study is to evaluate the effectiveness of tES (cathodal tDCS and 2hz tACS) improving the positive symptoms and negative symptoms associated with psychosis along with electrophysiology outcomes and motion perception.

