### **Description of Study Endpoints**

#### **Primary Endpoint**

Change from baseline in Positive and Negative Syndrome Scale (PANSS) total score after 1 week of tES. Change from baseline in SSVEP voltage after 1 week of tES. Change from baseline in Biological Motion task total score after 1 week of tES.

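### The primary objective claims effectiveness and the rationale claims target engagement, but with no sham or untreated control period no planned comparison isolates an effect of tES; the objective should be restated

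*Protocol*

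**What the plan says.** **Claim.** The Primary Objective section of the Protocol states: "The primary objective of this study is to evaluate the effectiveness of tES (cathodal tDCS and 2hz tACS) improving the positive symptoms and negative symptoms", and adds electrophysiology and motion perception. The Design and Statistical Methodology rows of the synopsis both pair effectiveness with feasibility, under the title "Feasibility Electrical Stimulation Study for Visual Hallucinations". Safety and tolerability come second, under Secondary Objectives. The Study Rationale says of two earlier case studies that "it is unclear whether the symptom reductions resulted from activity changes in the visual cortex or not", and then presents this trial as the one that will answer whether targeted stimulation can engage the target and improve symptoms.

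**Design.** The synopsis describes an "Open Label, Non-randomized, Crossover Design with Baseline, Day 5 and 1 Month follow up visits". Enrolment is "10 Individuals". The order is the same for everyone: "Participants first entered the cathodal tDCS condition first and then after a washout period (~2 weeks) entered the 2hz tACS condition". No sham or untreated control condition is described.

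**Endpoints and comparisons.** The first primary endpoint is "Change from baseline in Positive and Negative Syndrome Scale (PANSS) total score after 1 week of tES"; SSVEP voltage and the Biological Motion score are treated in the same way. The Statistical Methodology row and the Primary Analyses section plan two comparisons, within condition and between the two conditions, and rank neither. The only conditions named are the active ones: "before and after treatment conditions (cathodal tDCS and 2hz tACS".

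**The concern.** Effectiveness and target engagement are causal claims. They need a comparison in which stimulation is the only systematic difference, and neither planned comparison has that property. A Day 5 improvement could arise from stimulation, from the passage of time, from taking the same tasks again, or from participants and raters knowing that treatment was given. The rationale faults the earlier case studies because the source of their symptom reductions was unclear. This design leaves the source unclear too: SSVEP and symptoms could both move after five days without either movement being attributable to stimulation.

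At stake is what the trial may conclude. Under the present objective, a favourable change from baseline would answer the primary question, although the data cannot answer it.

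**Working it through.** The plan gives no alpha, sidedness, power, effect size or SD, so there is no figure of its own to reproduce. The main check is what each planned comparison can identify.

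**1. Within-condition change (baseline to Day 5).** The expected change is the stimulation effect plus the non-specific change. No planned comparison estimates the second term separately. Its likely parts differ by endpoint:

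| Endpoint | Time, fluctuation, repeat testing | Expectation | Rater knowledge |
|---|---|---|---|
| PANSS total (interview by clinical staff, no blinded rater stated) | yes | yes | yes |
| Biological Motion (computerised task, repeated) | yes, including practice | possible, weaker | does not score the task |
| SSVEP voltage | yes | weaker | does not score the voltage |

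**2. tDCS versus tACS.** Expectation and rater effects common to both conditions may partly cancel. What remains is the difference between two active effects, plus period, practice and any carryover from tDCS. With one fixed sequence these cannot be separated. Even a clean contrast would rank two active conditions; it could not show that either beats no stimulation.

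**3. Unstimulated intervals.** There are two: the washout of about 2 weeks, and the time to the 1-month visit, at which the Study Timeline shows no tES. Both follow active stimulation, and neither is planned as a control comparison.

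**4. Illustration of size.** From the Protocol: n = 10. Assumed: a paired t-test, two-sided 5%, a true stimulation effect of zero, and a non-specific change of d SDs of the change score.

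- Critical value: t(0.975, 9 df) = 2.262.
- Noncentrality: d × √10 = d × 3.162.
- Probability of a significant improvement: P(T > 2.262), with T noncentral t on 9 df.

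| d (assumed) | Noncentrality | Probability |
|---|---|---|
| 0 | 0 | 2.5% |
| 0.3 | 0.949 | 13.4% |
| 0.5 | 1.581 | 29.3% |
| 0.8 | 2.530 | 61.6% |

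These apply to one endpoint in one condition. Enrolling more people does not help: at d = 0.5 the probability is 56% with n = 20 and 87% with n = 40, because a larger sample estimates the same biased quantity more precisely.

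**The case against.** **Open-label feasibility studies are legitimate, and this one is candid about its design.** That stands. The title says feasibility, and the synopsis discloses the open label, the lack of randomisation and the 10 participants. A reader might infer that the trial is invalid without a sham arm. The documents do not support that; the fault is the mismatch between objective and design.

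**The Protocol contains unstimulated time.** Correct. A reader might infer that participants are never off stimulation, but the washout and the interval to 1 month show otherwise. What is missing is a control period.

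**The between-condition contrast removes some of the bias.** Partly so, for shared expectation. It brings in period, practice and carryover, and it answers a different question.

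**The biases do not bear equally on all endpoints.** This stands. Rater knowledge is chiefly a PANSS matter, and expectation explains an SSVEP change less well. Time and repeat testing remain for all three.

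**The harm is speculative and the figures are assumed.** Also largely right. No decision rule or success criterion says that a significant Day 5 change will be declared proof of efficacy, so that inference goes beyond the text. Nothing in the documents supports a non-specific change as large as 0.8 SD: a history of visual hallucinations suffices for entry, no PANSS threshold is set, and relevant antipsychotics must have been unchanged for a month. The planned methods are MMRM or non-parametric, not a paired t-test.

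**A separate SAP may deal with interpretation.** It may, but the objective and the control structure are fixed in the Protocol, and no analysis can supply the missing comparison.

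**Conclusion.** The point holds as a mismatch between claim and design. The synopsis, the rationale and the Primary Objective set out to evaluate effectiveness and target engagement, and neither planned comparison isolates an effect of tES. This follows from the design alone and depends on no numerical assumption.

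The probabilities of about 13%, 29% and 62% are illustration only. They rest on an assumed test, alpha, sidedness and size of non-specific change. They should not be read as the trial's error rates, nor 2.5% as a rate that the Protocol commits to. They show that moderate non-specific change would be enough to produce significant improvements under inert stimulation.

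The weakness is greatest for PANSS. It is narrower, but still present, for SSVEP and Biological Motion. The wording should be changed; the design need not be.

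**What to change.** Restate the aim in the synopsis Design and Statistical Methodology rows, the Study Rationale and the Primary Objective along these lines: *to assess the feasibility and tolerability of tES and to estimate, with 95% confidence intervals, the change from baseline in PANSS total, SSVEP and Biological Motion under each open-label condition.* Bring the Secondary Objectives into line, since tolerability now sits there.

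Add one sentence stating that neither the within-condition changes nor the fixed-order difference between conditions will be interpreted as evidence of efficacy or of causal target engagement.

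The cost is wording only: no added participants, visits, procedures or change to treatment. The downside is a less favourable stated conclusion.

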### **Secondary Objectives**

The secondary objective of the study is to evaluate the safety and tolerability of tES as well as secondary clinical outcomes including depression and global functioning and other visual domains.

**Clinical Outcomes:** Symptom ratings will be collected using the Montgomery-Asberg Depression Rating Scale, Global Assessment of Functioning, Positive and Negative Syndrome Scale

**Electrophysiology Outcomes:** To probe the oscillatory capacity of the visual cortex (i.e., visual sensory integration), a steady state visual evoked potentials (ssVEP) task will be implemented. Addiotnally, participants will be asked to perform an emotional response VEP using the International Affective Picture System (IAPS).

**Computerized visuoperceptual tasks:** The following visual perceptual functions will be evaluated: visuospatial working memory, velocity discrimination, biological motion

## **Diagnostic Assessments**

### **Structured Clinical Interview for DSM-IV (SCID)**

This is a structured clinical diagnostic screening interview for subjects 15 and older. It is used to diagnose Axis I disorders including modules on depression, mania, psychosis, alcohol and substance use, anxiety, somatic and eating disorders.

This will also be used when possible to confirm the diagnosis of schizophrenia in the first degree family member for the familial high risk group. Interview with a knowledgeable family member or copy of medical record is also acceptable to confirm the diagnosis.

It is possible that a potential participant is referred to this study from one of our other studies. In this case, if a previous diagnostic interview was done using the SCID then the clinician should obtain a BIDMC Release of Medical Information between the SPARCS study and the other study so the original SCID can be used as long it is updated. Be sure to check with the original study for the authorization dates to be used on the release (from the start of their participation in that study until study completion) so the correct dates are added to the release of information form. Depending on the length of time since the original SCID modules should be updated as needed. If longer than a month since the original SCID then the following updates should be done for:

1. Major depressive and manic symptoms in the past 30 days in the affective module A.
2. Inquire if there have been other mood episodes since the last SCID and determine if there has now been a past “worst” episode of depression or mania; if so evaluate past affective episodes.
3. Inquire if there has been a change in psychotic symptoms since the last SCID.
4. Inquire about current alcohol and substance use and evaluate for abuse or dependence if needed.
5. Inquire if there have been any changes in the anxiety, PTSD, somatic or eating disorders modules.

## **Clinical Assessments**

### **Positive and Negative Symptom Scale (PANSS)**

The ratings are based on a clinical interview, conducted by trained clinical staff, covering all of the items in the rating scale.

- This rating scale is meant to capture many different types of symptoms including positive, negative and general psychopathology symptoms. The ratings are based on a clinical interview with the participant.
- All items are completed for the past week.
- **Always use the manual** with anchor points when scoring and do not try to score from your memory of the anchor points or by their headings (mild, moderate or severe).

### **Montgomery and Asberg Depression Rating Scale (MADRS)**

#### **Interviewer:**

The questions in bold for each item **should be asked exactly as written**. Often these questions will elicit enough information about the severity and frequency of a symptom for you to rate the item with confidence. Follow-up questions are provided; however, for use when further exploration or additional clarification of symptoms is necessary. The specified questions should be asked until you have enough information to rate the item confidently. In some cases, you may also have to add your own follow-up questions to obtain necessary information.

*\*Ratings should be based on the patient's condition in the past week.*

**Referent of "usual" or "normal" condition.** Several of the interview questions refer to the patient's usual or normal functioning. In some cases, such as when the patient has Dysthymia or Seasonal Affective Disorder, the referent should be to the last time they felt OK (i.e., not depressed or high) for at least a few weeks.

*\*Rate the highest level of psychopathology. When in doubt, rate up and record the higher score.*

### **Global Assessment Functioning (GAF)**

Consider psychological, social, and occupational functioning on a hypothetical continuum of mental health-illness. Do not include impairment in functioning due to physical (or environmental) limitations.

Indicate appropriate code for the **LOWEST level of functioning during the week of POOREST functioning in past month**. (Use intermediate level when appropriate, i.e., 45, 68, 72).

[figure not shown]

## Visual Hallucinations Montages:

Ensure to mark electrodes for stimulation and that correct settings are adjusted on tES device.

